8.1 Screening

Screening

A screening period of up to 2 weeks will be used to assess patient eligibility. The screening period starts with the signing of the informed consent.

A BCVA assessment, as well as a complete ophthalmic examination, which may include slit-lamp exam, IOP measurement and fundus exam will be performed on both eyes. SD-OCT, OCTA, FA, ICGA and 3-field CFP are to be performed on both eyes and the diagnosis of active subfoveal CNV secondary to wAMD is to be confirmed in the study eye. The study Investigator will also collect vital signs (blood pressure and pulse). Medical history, demographic features and prior/concomitant medications are also to be collected. A serum pregnancy test is to be performed in women of childbearing potential.

One-time re-screening of patients is allowed, except for the purpose of capturing new BCVA or imaging assessments that previously failed to qualify the patient. As long as testing can be repeated within 14 days of the first screening, the other screening assessments do not need to be repeated. If re-screening is to occur beyond 14 days from the original screening visit date, then all screening procedures must be repeated. Medical judgment should be exercised to ensure that treatment of wAMD is not withheld in order for a patient to participate in the study.

8.1.1 Information to be collected on screening failures

Participants who sign an informed consent form and subsequently found to be ineligible will be considered a screen failure. The reason for screen failure should be recorded on the appropriate eCRF page. The demographic information, informed consent, and Inclusion/Exclusion eCRF pages must also be completed for screen failure participants. No other data will be entered into the clinical database for participants who are screen failures, unless the participant experienced a serious adverse event (SAE) during the screening phase (see [Section 10.1.3](#) for reporting details).

8.2 Participant demographics/other baseline characteristics

The following information will be collected/documentated at Screening/Baseline visit for each participant:

- Age (Screening)
- Sex (Screening)
- Race/Ethnicity (Screening)
- Vital signs, i.e. sitting blood pressure (systolic and diastolic pressure in mmHg) and pulse rate (beats per minute) (Screening and Baseline). Of note, in case there is an elevated blood pressure measurement as specified in the exclusion criteria, at Screening, the blood pressure measurement should be repeated after 20 minutes. If the repeat measurement is elevated as specified in the exclusion criteria, then the patient is not eligible to be enrolled into the study.

- Pregnancy test results for all women of childbearing potential (Screening and Baseline)
- Visual acuity (BCVA) (Screening and Baseline)
- Complete ophthalmic examination (Screening and Baseline)
- Retinal imaging (SD-OCT, OCTA and 3-field CFP at Screening and Baseline; FA and ICGA at Screening)
- EQ-5D-5L questionnaire (Baseline)
- HADS questionnaire (Baseline)
- Prior/concomitant medications (all prescription medications, over-the-counter drugs and significant non-drug therapies must be documented. See [Section 6.2.1](#) for further details) (Screening and Baseline)
- Medical history and current medical conditions (Screening)

Investigators will have the option to record abnormal test findings on the medical history eCRF page whenever, in their judgment, the test abnormality occurred prior to the informed consent signature.

8.3 Efficacy

The following assessments will be performed to assess the predictive value of early anatomical parameters measured by multimodal imaging at each visit from Baseline to Week 16 in q12w fluid-free participants (i.e. participants without IRF and SRF at Week 48 who have maintained a stable q12w treatment regimen up to Week 48 after the loading phase), as well as to evaluate the effect of brolucizumab on visual function, retinal structure, vascular leakage, quality of life and anxiety and depressive status:

- CNV lesion type assessed by FA, CFP and ICGA at Screening and SD-OCT at Baseline
- OCTA parameters, of which the main quantitative parameters are CNV flow size and vessel density and the main qualitative ones are branching vessels, peripheral anastomotic arcades, vascular loops and dark halo (from Baseline to Week 48)
- SD-OCT parameters, of which the main quantitative parameters are CRT and PED volume, and the main qualitative ones are IRF, SRF, sub-RPE fluid, status of the ELM, SHRM and outer retinal tubulation (from Baseline to Week 48)
- FA and ICGA (at Screening and Week 48)
- 3-field CFP (from Baseline to Week 48)
- BCVA with ETDRS-like charts at 4 meters (from Baseline to Week 48)
- EQ-5D-5L questionnaire (at Baseline and Week 48)
- HADS questionnaire (at Baseline and Week 48)

All efficacy assessments should be performed prior to any administration of study treatment.

8.3.1 Fluorescein angiography and indocyanine green angiography

Fluorescein angiography (FA) and indocyanine green angiography (ICGA) will be performed in both eyes at Screening and Week 48. All FA and ICGA images will be obtained by trained and study-certified site personnel at the study sites and evaluated by the Investigator according to his/her standard of clinical practice to confirm the diagnosis of wAMD at Screening. Certification of the equipment and examiners at each investigative site will occur prior to evaluation of study participants.

For the purpose of screening, FA and ICGA images from previous routine evaluations may be used as long as FA was performed within 3 days of the Screening visit using CRC-certified equipment and technician/Investigator.

A treatment regimen-masked Central Reading Centre (CRC) will be used in this study. The CRC will provide sites with a Study Manual and training materials for the specified study ocular images. Before any study images are obtained, site personnel, test images, systems and software will be certified and validated by the CRC as specified in the Study Manual. FA and ICGA screening images and FA images at week 48 will be forwarded to the CRC for independent standardized analysis. The CRC data will be used for the evaluation of the objectives comprising the assessment of FA and ICGA parameters (i.e. to classify the type of CNV lesions) to ensure a standardized evaluation. Further details about all parameters to be evaluated by the CRC are reported in the CRC grading charter (a separate document). The CRC will create a database with the agreed variables as indicated in the CRC charter and will transfer the data from this database to Novartis/CRO for analysis.

Additional images will be taken in case of any signs of intraocular inflammation. Fluorescein angiography should be performed for safety evaluation as described in Section 8.4.2. and uploaded onto the CRC portal.

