FA remains the gold standard for the diagnosis and classification of CNV, as it allows the visualization of retinal vasculature and neovascular retinal/choroidal proliferations as well as its dynamic features, such as perfusion and exudation (Schmidt-Erfurth et al., 2014). ICGA can be used to identify the entire extension of the CNV lesion due to its capability to visualize the sub-RPE components of the CNV (Sulzbacher et al., 2011). Besides, ICGA allows a better identification of the neovascular network of type 1 CNV lesions and is also useful in the diagnosis of RAP and polypoidal choroidal vasculopathy (PCV), which is a subtype of type 1 CNV characterized by a large aneurysmal component. Both FA and ICGA are invasive and require dye injection (Gess et al., 2011).

OCT is a noninvasive imaging technique able to visualize structural changes of the neurosensory retina and the RPE through high-resolution cross-sectional (tomographic) images (B-scans). OCT has changed the diagnostic approach to wAMD. Current commercial OCT systems based on the spectral domain technology, i.e. spectral-domain OCT (SD-OCT), allow dense scanning of the macula with an improved axial resolution. SD-OCT is widely used to support the initial diagnosis of CNV obtained from FA and ICGA, as it allows to define the morphological features of the CNV complex, such as retinal thickening, and to detect early signs of CNV activity, such as intraretinal (IRF), subretinal (SRF) and under RPE (sub-RPE) fluid, intraretinal cystoid spaces and PED, as well as edema. Thus, through SD-OCT it is possible to qualitatively and quantitatively define these wAMD anatomical changes, as well as to measure the thickness of the retina. Moreover, SD-OCT scans performed at different time points with the same instrument can be compared over time to follow the progression/regression of the lesions (Keane et al., 2012).

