At the Baseline visit (Day 1), after confirmation of eligibility, patients will be included and treated with intravitreal (IVT) brolucizumab at the dose of 6 mg. Only one eye could be treated in the study. Participants will receive three monthly loading doses of brolucizumab 6 mg at Baseline, Week 4 and Week 8, followed by a maintenance regimen every 12 weeks (q12w), which may be adjusted to a treatment regimen every 8 weeks (q8w) if disease activity (DA) in the study eye is detected according to Investigator's decision based on the disease activity assessments (DAAs) of visual and/or anatomical outcomes performed by the Investigator him/herself ("q12w/q8w regimen"). DA will be first assessed at Week 16 and then at each subsequent scheduled q12w/q8w treatment visit. In participants on q12w treatment regimen with DA occurrence at any of these visits, a q8w treatment regimen should be considered. If a

participant is adjusted to a q8w treatment regimen, he/she will subsequently be assessed at q8w treatment visits. In participants on q8w regimen without DA for two consecutive treatment visits, based on the Investigator's judgment, the re-allocation to a q12w treatment regimen should be considered. DAAs are to be performed by the Investigator based on visual acuity (BCVA) and/or 3-field CFP and/or one or more anatomical parameters assessed by SD-OCT and/or by OCTA, as per clinical practice. Of note, only those anatomical parameters that are instrumental to define DA in the Investigator's opinion will be recorded in the eCRF. All anatomical parameters collected by SD-OCT and OCTA throughout the study and by FA, ICGA (only for suspected PCV) and CFP at Screening and Week 48 (FA only) will be evaluated by an independent, treatment regimen-masked Central Reading Center (CRC) for the primary and secondary analyses at the end of the study. Of note, the Investigator will not be aware of the results of the CRC assessments during the study. For all participants, the last potential study treatment will be at the Week 44 visit or at the Week 48 visit, according to the different treatment regimen implemented.

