A study visit schedule will be established at Baseline for all participants. The mandatory visits of the study during the treatment period for all participants are Baseline, Week 4, Week 8, Week 12 (no injection visit), Week 16 and Week 48. The timepoint of the other treatment visits will depend on the treatment regimen of each participant (q12w/q8w). BCVA assessment, SD-OCT, OCTA and 3-field CFP imaging are to be performed on the study eye at each assessment visit, as well as a urine pregnancy test in women of childbearing potential. FA and ICGA are to be performed at Week 48. Concomitant medications and any adverse events are to be recorded throughout the study. A complete ophthalmic examination, which may include slit lamp exam, fundus exam and IOP measurement and the collection of vital signs are to be performed at Baseline and at each subsequent visit by the Investigator. At each visit the Investigator have to exclude the presence of any active intraocular inflammation in the study eye. A complete ophthalmic examination is also to be performed at Week 48. Besides, IOP measurement is to be performed before and after each IVT injection. Patient's anxiety/depression and quality of life will be evaluated at Baseline and Week 48 through the Hospital Anxiety and Depression Scale (HADS) and the EuroQol-5D-5L (EQ-5D-5L), respectively. BCVA, SD-OCT, CFP, OCTA, FA, ICGA, ophthalmic examination and IOP measurement are also to be performed on the fellow eye at Week 48. No monitoring visits are planned between the injection visits. All efforts should be made to adhere to this study visit schedule within a \pm 7-day window (except Baseline). For a given protocol visit (except Baseline), assessments can be performed on two consecutive days, provided both days are within the \pm 7-day window. Treatment is intended to be administered on the day of study visit, or if this is not possible, within 3 days after the study visit at which the per-protocol assessments have taken place (except Baseline, in which case study treatment administration should occur within the next 24 hours). Two consecutive study treatments should be at least 21 days apart.

4 Rationale

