14. Aphakia with the absence of posterior capsule in the study eye.

Systemic conditions and treatments

15. Stroke or myocardial infarction in the 6-month period prior to Baseline.
16. End stage renal disease requiring dialysis or renal transplant.
17. Uncontrolled blood pressure defined as a systolic value \geq 160 mmHg or diastolic value \geq 100 mmHg at Screening or Baseline. (In case there is an elevated blood pressure measurement, it should be repeated after 20 minutes. If the repeat measurement is elevated, then the patient is not eligible to be enrolled into the study).
18. Systemic anti-VEGF therapy at any time.
19. Systemic medications known to be toxic to the lens, retina or optic nerve (e.g. deferoxamine, chloroquine/hydroxychloroquine, tamoxifen, phenothiazines and ethambutol) used during the 6-month period prior to Baseline except temporary use for COVID-19 treatment.
20. History of hypersensitivity to any of the study drugs or their excipients or to drugs of similar classes, or clinically relevant sensitivity to fluorescein dye as assessed by the Investigator.
21. History of malignancy of any organ system (other than localized basal cell carcinoma of the skin or *in situ* cervical cancer), treated or untreated, within the past 5 years, regardless of whether there is evidence of local recurrence or metastases.
22. History of a medical condition (e.g. metabolic dysfunction disease with exception of type 1 or 2 diabetes mellitus, physical examination finding, or clinical laboratory finding) that, in

the judgment of the Investigator, would preclude scheduled study visits, completion of the study, or a safe administration of investigational product.

23. Use of systemic investigational drugs within 5 half-lives of baseline or within 30 days/until the expected pharmacodynamic effect has returned to baseline, whichever is longer; or longer if required by local regulations (observational clinical studies solely involving over-the-counter vitamins, supplements, or diets are not exclusionary).

Other

24. Not interpretable OCTA and SD-OCT images according to Investigator's clinical judgment at Screening in the study eye
25. Pregnant or nursing (lactating) women, where pregnancy is defined as the state of a female after conception and until the termination of gestation, confirmed by a positive hCG pregnancy test.

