6.7.2 Instruction for prescribing and taking study treatment

The study consists of a treatment period with brolucizumab from Baseline (Day 1) up to Week 48, as shown in [Figure 6-1](#).

Figure 6-1 Treatment regimen

As per Beovu® SmPC, the recommended dose of 6 mg brolucizumab (0.05 ml solution) is to be administered by intravitreal injection every 4 weeks (monthly) for the first 3 doses. Thereafter, the Investigator may individualize treatment intervals based on DA in the study eye as assessed by visual acuity and/or anatomical parameters (BCVA and/or IRF, SRF, sub-RPE fluid, hemorrhage, CRT and/or OCTA parameters and/or 3-field CFP). A first DA assessment is to be performed at Week 16, as recommended in Beovu® SmPC. In participants without DA, treatment every 12 weeks (q12w) should be considered. In patients with DA, treatment every 8 weeks (q8w) should be considered. DA will be first assessed at Week 16 and then at each subsequent scheduled q12w/q8w treatment visit. In participants on q12w regimen with DA at any of these visits, a q8w treatment regimen should be considered. In participants on q8w regimen without DA for two consecutive treatment visits in the opinion of the Investigator, the re-allocation to a q12w regimen should be considered.

Regardless of treatment administration, Baseline, Week 4, Week 8, Week 12, Week 16 and Week 48 visits are mandatory for all participants. The timepoints of the other treatment visits will depend on the treatment regimen of each participant (q12w/q8w). No monitoring visits are planned between the injection visits.

For all participants, the last potential study treatment will be at the Week 44 visit or at the Week 48 visit, according to the different treatment regimen implemented.

The different types of visits occurring through the study are summarized in [Table 6-3](#) with a description of when disease activity assessment and treatment take place.

Table 6-3 Disease activity assessment and treatment occurrence according to visit type

Type	Disease Activity Assessment	Treatment
Screening visit	No	No
Baseline (Day 1) visit	No	Yes
Week 4 and 8 visits	No	Yes
Week 12 visit	No	No

Type	Disease Activity Assessment	Treatment
Week 16 visit	Yes	Yes (if DA is present)
Treatment visits (every 8 or 12 weeks according to Investigator's decision)	Yes	Yes (every 8 or 12 weeks according to Investigator's decision)
Week 48 visit	Yes	Only if a treatment was planned at the visit, based on treatment regimen

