Visit number	1	2	3	4	5	6	7-13	14
Weeks	Up to 2 weeks	1	4	8	12	16	20 to 44 ¹	48
Obtain informed consent	X							
Demography	X							
Inclusion/exclusion criteria	X	X						
Relevant medical history/current medical history	X							
Vital Signs ^{2, 3}	X	X	X	X	X	X	X	X
Prior/Concomitant systemic medications	X	X	X	X	X	X	X	X
Prior/Concomitant ocular medications	X	X	X	X	X	X	X	X
Serum β-hCG Pregnancy Test ⁴	X							
Urine Pregnancy Test ⁴		X	X	X	X	X	X	X
BCVA score (ETDRS)	X	X	X	X	X	X	X	X
IOP measurement ⁵	X	X	X	X	X	X	X	X
Complete ophthalmic examination ^{2, 6}	X	X	X	X	X	X	X	X
SD-OCT ⁹	X	X	X	X	X	X	X	X
OCTA	X	X	X	X	X	X	X	X
FA ⁹	X							X
ICGA	X							X
Color Fundus Photography (CFP)	X	X	X	X	X	X	X	X
EQ-5D-5L		X						X
HADS		X						X

Period	Screening	Treatment						End of Study
Visit Name	Screening*	Baseline Day 1	W4	W8	W12	W16	Treatment visits	W48*
Visit number	1	2	3	4	5	6	7-13	14
Weeks	Up to 2 weeks	1	4	8	12	16	20 to 44 ¹	48
Disease Activity Assessment ⁷						X	X	X
Study drug administration		X	X	X		X ⁸	X ⁸	X ⁸
Adverse Events	X	X	X	X	X	X	X	X

X = assessment to be recorded in the clinical database or received electronically from a vendor

* At Screening and Week 48 the fellow eye will be assessed for BCVA, ophthalmic examination, IOP, SD-OCT, OCTA, CFP, FA and ICGA. For the other visits it will be assessed according to clinical practice

¹ Treatment visits will take place every 8 or 12 weeks starting from Visit 4 (Week 8), according to Investigator's decision at each assessment visit

² Vital signs collection and/or complete ophthalmic examination are to be performed at each visit. The Investigator have to exclude the presence of any active intraocular inflammation in the study eye.

³ Vital signs include sitting blood pressure and pulse rate.

⁴ Women of childbearing potential only. A positive urine test should be confirmed by a Serum β-hCG Pregnancy test.

⁵ IOP measurement is to be performed prior and 30-60 minutes after each treatment IVT injection

⁶ Complete ophthalmic examination include slit lamp exam, IOP measurement and fundus exam, for safety assessment before and after IVT. Pupil dilation optional according to local practice.

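### Week 48 indocyanine green angiography is scheduled without condition, yet the specific central-reading statements leave it out and no planned endpoint or analysis uses it

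*Protocol*

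**What the plan says.** On performing the test, Protocol Section 8.3.1 states: "Fluorescein angiography (FA) and indocyanine green angiography (ICGA) will be performed in both eyes at Screening and Week 48". Section 3 says "FA and ICGA are to be performed at Week 48". Table 8-1 marks ICGA at Screening and at Week 48, and its footnote adds: "At Screening and Week 48 the fellow eye will be assessed for BCVA, ophthalmic examination, IOP, SD-OCT, OCTA, CFP, FA and ICGA". Section 8.3 lists Week 48 ICGA among the efficacy assessments, Section 8.5.2 repeats it for the fellow eye, and SAP Section 3.4 reproduces the schedule. Section 6.7.2 makes the visit compulsory: "Regardless of treatment administration, Baseline, Week 4, Week 8, Week 12, Week 16 and Week 48 visits are mandatory for all participants".

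On reading the images, Section 8.3.1 says "FA and ICGA screening images and FA images at week 48 will be forwarded to the CRC for independent standardized analysis". Section 3 describes the centrally evaluated material with the words "ICGA (only for suspected PCV) and CFP at Screening and Week 48 (FA only) will be evaluated by an independent". Section 8.5.2 has the fellow-eye images sent to the reading centre for storage and mentions no grading.

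On burden, Section 1.1 says "Both FA and ICGA are invasive and require dye injection".

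**The concern.** A study-mandated invasive procedure should have a stated purpose: a reader, an endpoint, a safety use or a decision that depends on it. For Week 48 ICGA the documents give the instruction to perform the test but no planned use of the result. Participants would carry the burden of a dye test that no planned analysis draws on. Sites would also face conflicting text on whether everyone has the test and whether the images are graded.

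The stake is participant burden and consistency of the protocol. The primary and secondary results do not depend on it.

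**Working it through.** No figure in the plan has to be reproduced. The check traces ICGA, with FA for comparison, through performance, central reading and use.

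| | Performed | Sent for central analysis (Sections 3 and 8.3.1) | Planned endpoint or analysis |
|---|---|---|---|
| ICGA, Screening | Yes | Yes (Section 3 adds a suspected-PCV qualifier) | Yes: lesion type |
| ICGA, Week 48 | Yes, no condition in the schedule | No | None |
| FA, Screening | Yes | Yes | Yes: lesion type; SAP 6.2 summary |
| FA, Week 48 | Yes | Yes | None |

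**Who has it.** Sections 3, 8.3, 8.3.1 and 8.5.2, Table 8-1 and SAP 3.4 attach no condition. Part of the Table 8-1 footnotes is blacked out, but the footnote mark without visible text (9) stands on the SD-OCT and FA rows and not on the ICGA row. Under Section 9.1.1, participants who stop treatment keep their assessments apart from the disease activity assessment and injection-related items. Under Section 8, those who leave the study early are asked to have all final-visit assessments. Against this stands the Section 3 parenthesis on suspected polypoidal choroidal vasculopathy (PCV). It occurs in a sentence about central evaluation, so it may limit reading or performance. No procedure section repeats it.

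**Who reads it.** Sections 3 and 8.3.1 are the two statements that separate time points by modality, and both confine Week 48 to FA. Section 6.4 speaks generally of central reading of all five modalities at predefined time points and refers to Table 8-1, where ICGA is marked at Week 48. That sentence cannot be taken literally: it covers color fundus photography (CFP) too, which Table 8-1 marks at every visit, while Section 8.3.4 forwards only the screening photographs for central analysis.

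**What uses it.** Protocol Table 2-1 and Section 12 bring ICGA in through CNV lesion type at Screening. SAP 6.3.1 does the same, with lesion type as a candidate predictor timed at Screening. Lesion type also appears in the SAP's dropout model (6.3.1), the baseline description (6.2), the CST and BCVA plots (6.3.2.2 and 6.3.2.3) and the Week 12 groupings (6.3.2.5). None of these is a Week 48 ICGA variable. Leakage on FA or ICGA appears in SAP 2, 6.3.2.5 and 6.6 as a parameter the Investigator may have used for disease activity, but it is analysed only for the Week 16 regimen choice. Count of planned Week 48 ICGA variables: 0.

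**How many.** SAP 3.1 gives 122 enrolled against 263 planned. One Week 48 ICGA examination each gives at most 122 × 1 = 122, less those who never attend. If the PCV remark limits performance, the number is that of suspected cases, which the documents do not give, so it lies anywhere from 0 to 122.

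**Timing.** SAP 6.6 sets the interim cut-off at the last enrolled patient's Week 16 visit and gives it as 16 February 2023. Week 48 is 48 − 16 = 32 weeks, or 224 days, later: 28 September 2023. Allowing the ±7-day window at both visits gives 14 September to 12 October 2023. The SAP is dated 28 November 2023.

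**The case against.** The strongest reply is that the plan does not rule out a use for the images. Section 8.3 lists Week 48 ICGA under aims that include vascular leakage. Section 6.4 can be read as covering its central reading. The parameters to be graded sit in a reading centre charter that is a separate document. The Investigator makes a disease activity assessment at Week 48, and the SAP recognises leakage on FA or ICGA as one basis for such an assessment. This stands far enough to block a stronger conclusion that a reader might draw: that nobody reads the test, or that it cannot contribute to any result. The documents support only that no planned endpoint or analysis uses it and that the specific reading statements omit it. The leakage aim has no matching endpoint, and the protocol's own disease-activity lists (Table 8-1 footnote 7 and Section 8.3.6) do not name ICGA.

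A reader might also infer that every participant certainly has the test. The PCV remark in Section 3 leaves that open.

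Two further inferences fail. The exclusion for "clinically relevant sensitivity to fluorescein dye" names only one of the two dyes, but this applies equally to Screening ICGA, so it gives no reason to drop the Week 48 test. The merging of PCV with Type I in the SAP's primary model concerns Screening; PCV is still reported separately at baseline and lesion type is used elsewhere.

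Finally, Week 48 FA also lacks a planned endpoint or analysis, so the problem is not peculiar to ICGA. That is correct, and the fix covers FA. The difference is that Week 48 FA is at least sent for central grading.

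**Conclusion.** The point holds in limited form. Week 48 ICGA is scheduled without condition, is excluded by both specific central-reading statements, and has no planned endpoint or analysis. The passages conflict on who has it and whether it is read. The size is up to 122 participants (263 as planned) if the schedule is taken literally, and fewer by an unknown number if the PCV remark limits performance. No planned estimate, test or conclusion changes.

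This rests on the protocol and SAP text alone. A reading centre charter that specifies grading of Week 48 ICGA would answer the question of reading, though not the absence of an analysis.

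**What to change.** Reconcile Protocol Sections 3, 6.4, 8.3, 8.3.1 and 8.5.2, Table 8-1 with its fellow-eye footnote, and the SAP 3.4 copy. They should state for whom Week 48 ICGA is done, whether it is graded, and which endpoint or purpose it serves. Unless these are stated, remove ICGA from the study-mandated Week 48 assessments in both eyes. Keep Screening ICGA for lesion typing. Whether an individual patient has ICGA for clinical reasons stays with the investigator.

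State the purpose of Week 48 FA as well, either by adding the analysis it is meant to serve or by saying that none is planned.

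The cost is a wording change. What is lost is a set of stored Week 48 ICGA images for unplanned use. On the dates above, the Week 48 visits were probably over before the SAP was final. For this trial the remaining step is then likely documentary: the SAP or study report should say how many participants had Week 48 ICGA and FA and how those images are handled.
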